The overall objective of this multicenter trial is to determine whether use of a low-cost, high-resolution microendoscope during diagnostic upper endoscopy can improve the efficiency and accuracy of endoscopic screening for esophageal squamous cell neoplasia (ESCN). This is a trial of a novel technology, a miniaturized, low cost (<\$3,500) microscope device which can be used during upper endoscopy to image the gastrointestinal epithelium. This portable, battery-operated high-resolution microendoscope (HRME) was developed by our collaborators at Rice University and provides greater than 1000X magnified images of the esophageal mucosa. In a single-arm, pilot study of the device in an enriched population of 60 high-risk subjects in China and the US, we used the microendoscope during routine Lugol's chromoendoscopic screening to categorize areas of abnormality (unstained areas). The sensitivity /specificity for the device seen in this study were 100% and 79%-a significant improvement over the sensitivity/specificity of Lugol's chromoendoscopy which were 97% and 52%. Thus, our presumption is that HRME can enhance the specificity (and lower the false positive rate) of Lugol's. As part of a National Cancer Institute R01 supplement (Figure 1), we have enhanced the current HRME technology by introducing an automated, ergonomic, augmented reality platform. The augmented reality platform displays, in real-time, the microscopic image colocalized with the endoscopic image, potentially allowing more targeted biopsies/treatment and increased accuracy. Our central hypothesis is that our approach can improve the efficiency and clinical impact of endoscopic screening and surveillance of ESCN by providing *in-vivo* optical biopsies comparable to standard histology. Specifically, HRME will facilitate accurate, rapid real-time endoscopic screening by non-expert clinicians. We also hypothesize the HRME will provide additional, more accurate information regarding the presence of neoplasia that will impact upon the physician's decision to obtain a mucosal biopsy or perform endoscopic therapy (endoscopic mucosal resection or ablation). This could potentially minimize the number of unnecessary biopsies and enable the physician to perform endoscopic therapy at the time of the initial examination, rather than delaying endoscopic treatment to another procedure following pathologic confirmation of the initial biopsies. We will compare (1) the current endoscopic "standard of care" (white light endoscopy with Lugol's iodine), (2) HRME with subjective, human interpretation, and (3) augmented reality HRME (software, 'machine' interpretation). The addition of (3) is the basis for our revision R01 and this amended IRB. The accuracy, efficiency, clinical impact and cost-effectiveness of each approach in the diagnosis and management of ESCN will be determined in both the Chinese and US healthcare systems. Specific endpoints: 1. Efficiency: (a) Diagnostic Yield: The number of neoplastic biopsies/total number of biopsies obtained in patients who receive biopsies. (b) 'Patients saved': Number of patients who receive no biopsies (c) Procedure time: Total procedure time in each group 2. Clinical impact: Determine potential clinical impact of HRME by determining if use of the device (with both subjective and automated read) changes the decision to perform endoscopic therapy and perform, or not perform, a mucosal biopsy when compared to LC alone. 3. Prospectively compare the performance characteristics of HRME-LC to LC for the prediction of squamous esophageal neoplasia in flat mucosa and mucosal lesions using histopathology as the gold standard. (a) Determine the sensitivity, specificity, positive and negative predictive value for the identification of neoplasia on a per biopsy and per patient analysis. 4. Determine the cost-effectiveness of HRME-LC to LC alone for the endoscopic screening and surveillance of ESCN in the US and China.

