All-inclusive outpatients undergoing routine (standard of care) Lugol's chromoendoscopic evaluation for suspected or known squamous cell neoplasia will be enrolled as well as any outpatients referred to the clinic with any prior history of squamous cell dysplasia and/or neoplasia will also be considered eligible as they will serve as study population for the surveillance group. Patients seen in outpatient clinics who are high risk for esophageal dysplasia/neoplasia, including patients with known history of head/neck cancer or of Northern Chinese descent will also be eligible for enrollment.

Six novice and four expert endoscopists will be the research subjects for the post hoc image analysis project. The subjects will be practicing endoscopists or GI fellows at current study sites or other institutions.

Exclusion Criteria:

- Allergy or prior reaction to the fluorescent contrast agent proflavine - Patients who are unable to give informed consent - known advanced squamous cell carcinoma of the distal esophagus, or dysplastic/suspected malignant esophageal lesion greater than or equal to 2cm in size not amenable to endoscopic therapy - Patient unable to undergo routine endoscopy with biopsy: - women who are pregnant or breastfeeding - prothrombin time greater than 50% of control; PTT greater than 50 sec, or INR greater than 2.0 - inability to tolerate sedated upper endoscopy due to cardio-pulmonary instability or other significant medical issues

F2. Procedure

Written informed consent will be obtained prior to study participation using the IRB-approved consent form.

The patient will be assigned to one of two groups: Group A: HRME-LC (HRME + Lugol's) or Group B (Lugol's alone). Randomization assignments (HRME-LC vs. LC) will be computer-generated with allocation concealment using sealed envelopes. As part of the NCI R01 supplement, the HRME-LC arm will now include the augmented reality HRME component following the standard HRME image. The Augmented Reality (AR) glasses will allow the endoscopist to see the microendoscopic (HRME) and endoscopic image at the same time. We now can produce a colocalized image that can be seen on the glasses at the same time as the endoscopic image AND in the same field of view. This does NOT change patient care. Rather, it improves the visualization of the endoscopist as shown in Figure 1.

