In both groups, per standard of care, endoscopic examination will be performed using white-light endoscopy with Lugol's dye-spray. In each subject, the location of each unstained area (level, quadrant) will be recorded and digital images obtained. The endoscopist's clinical impression will be recorded for each Lugol's abnormal area and visible lesion ('nonneoplastic' vs. 'neoplastic') as well as his/her proposed plan: a. no biopsy, b. biopsy, c. endoscopic treatment/removal. In the standard-of-care arm (Group B), biopsies will be obtained of all Lugol's abnormal areas. Likewise, Group A will receive the clinician subjective HRME read + augmented reality software HRME read, sequentially, of all Lugol's unstained (abnormal) areas prior to tissue biopsy. For imaging, 1-10 ml proflavine hemisulfate (0.01%) will be sprayed on the esophageal mucosa. The HRME probe placed gently on the mucosa and the augmented reality microscopic (HRME) image displayed on the glasses, with the endoscopic image (monitor) behind it. The endoscopist will first make a subjective interpretation (neoplasia vs. no neoplasia) and plan of action (biopsy, no biopsy, treat) WITHOUT the image-analysis software. Once this qualitative ("Human") read is recorded, the image analysis software will be turned on and the software diagnosis provided in real-time. This quantitative ("Machine") read and the revised plan of action will be recorded. The HRME procedure (including Human and Machine reads) as well as standard endoscopy and biopsy time will be recorded. The research coordinators will indicate the biopsy number/location on an esophageal map diagram. The biopsies from each site will be placed in formalin per standard of care and labeled according to biopsy location (quadrant: 12, 3, 6, 9 o'clock). In all subjects, all Lugol's abnormal areas will be biopsied (to uphold the standard of care, per IRB); however, HRME "non-neoplastic" sites will be considered not tissue-biopsied for purpose of the analysis. All biopsies will be submitted for consensus diagnosis by 2 expert GI pathologists.

A schematic of the existing trial with the proposed revision is shown in Figure 2. The IRB revision is shown in RED. We anticipate that this revision will add an additional 30-60 seconds per procedure but will otherwise not change patient care.

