Diagnostic yield: This is defined as the proportion of all biopsies that are truly neoplastic over the total number of biopsies obtained in patients who receive biopsies. A generalized linear model for logistic regression with multiple correlated binary outcomes within each patient will be used for data analysis. In this model the binary outcome for each biopsy specimen is whether the specimen is neoplastic or non-neoplastic, and the explanatory variable is the arm (LCE+HRME vs. LCE alone) stratified by group (screening and surveillance). PROC GLIMMIX in SAS will be used because of the correlations among samples from the same patient. The model will allow for testing whether the proportion of samples classified as neoplasia differs between the 2 arms.

'Clinical efficiency': For patients that have benign disease confirmed by histology, the true proportion of patients potentially saved any biopsy using HRME (Lugol's + and HRME -) will be estimated by 95% confidence intervals (stratified by group). Proportions will be compared between groups by the chi-square test or Fisher's exact test. Procedure time in the HRME+LC arm will be compared to the LC arm by analysis of variance, stratified by group (screening and surveillance). An interaction term will also be included to determine to what extent the difference in procedure time between the 2 arms varies between the 2 risk groups.

Clinical impact: For this, the proportion of patients who had a change in the decision to perform endoscopic therapy or mucosal biopsies as a result of LCE+HRME or LCE alone, will be estimated by a 95% confidence interval. This proportion will be compared between LCE+HRME and LCE alone by the chi-square test or Fisher's exact test.

Progression rates: Five year follow-up of progression rates to more advanced pathology or esophageal cancer (EC) in the 2 arms will be conducted. Progression rates and their 95% confidence interval will be summarized and compared between LCE+HRME and LCE alone by the chi-square test or Fisher's exact test.

Safety/Adverse Events: Immediate and 48 hour adverse event (AE) rates will be compared between the LCE+HRME arm and LCE alone arm by the chi-square test or Fisher's exact test. The AE rates and their 95% confidence intervals will be summarized.

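### Clinical impact: the between-arm test of changed decisions has no described Group B counterpart; estimate change within Group A and keep any randomised comparison for final plans

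*Combined protocol and SAP*

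**What the plan says.** Section D, endpoint 2, asks whether the device, by subjective or automated read, alters the decision to treat endoscopically and to "perform, or not perform, a mucosal biopsy when compared to LC alone". The same section hopes that HRME will "enable the physician to perform endoscopic therapy at the time of the initial examination".

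Section G2 (Clinical impact) turns this into the "proportion of patients who had a change in the decision to perform endoscopic therapy or mucosal biopsies as a result of LCE+HRME" or Lugol's alone. It plans a 95% confidence interval for that proportion and then adds the test: "This proportion will be compared between LCE+HRME and LCE alone by the chi-square test" or Fisher's exact test. G2 lists clinical impact among the secondary analyses and states no alpha, expected rate or power for it.

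Section F2 describes how decisions are captured. In each subject of both arms, the endoscopist's impression "will be recorded for each Lugol's abnormal area and visible lesion", "as well as his/her proposed plan: a. no biopsy, b. biopsy, c. endoscopic treatment/removal". Group A then has a plan after the subjective HRME read and a revised plan after the software read. The software step is new with the revision: "the HRME-LC arm will now include the augmented reality HRME component following the standard HRME image". For Group B, the next step described is biopsy of every Lugol's-abnormal area. F2 also requires that biopsy in all subjects, whatever HRME shows.

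**The concern.** A between-arm comparison of change presupposes that each arm has a before and an after. The text gives Group A two or three decision points and Group B one. If Group B patients are entered as having no change, the test compares a measured proportion with a zero that the design imposes. If they are left out, there is nothing to compare.

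At stake is a secondary claim. A very small p-value could be reported as evidence of clinical impact when it shows only that some endoscopists changed some plans after a second look. The test is also blind to direction: moves from biopsy to no biopsy and moves the other way both add to the same count.

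**Working it through.** The plan gives no figure for this endpoint, so there is none to reproduce. The check is structural first, then numerical.

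**1. Decision points by arm (section F2).**

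| Step | Group A (HRME + Lugol's) | Group B (Lugol's alone) |
|---|---|---|
| After Lugol's | plan recorded | plan recorded |
| After human HRME read | plan recorded | not described |
| After machine read (post-revision) | revised plan recorded | not described |
| Tissue | all Lugol's-abnormal areas biopsied | all Lugol's-abnormal areas biopsied |

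A change can be computed in Group A only. Tissue taken cannot stand in for a second decision, because biopsy is mandated in both arms.

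**2. What the test does if Group B is set to zero.** Inputs: G1 gives 650 surveillance and 650 screening patients, and 325 per arm in screening. I infer 325 per arm in surveillance, hence 650 per arm overall. Two-sided alpha 0.05 is an assumption. With k changes in Group A, none in Group B and n per arm, the two-sided Fisher p-value is

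p = 2 × [n(n−1)…(n−k+1)] / [2n(2n−1)…(2n−k+1)],

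which is close to 2 × (1/2)^k when n is large relative to k.

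- k=5: approximation 2/32 = 0.0625; exact at n=650, p=0.062.
- k=6: approximation 2/64 = 0.031; exact at n=650, p=0.031; at n=325, p=0.031; at n=200, p=0.030.

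The threshold is therefore six changed patients, almost regardless of arm size. The uncorrected chi-square would reject at four (4/650 against 0/650, p=0.045), but the expected counts are then 2 per arm, so Fisher's test would normally be used.

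**3. Chance of rejection.** This is P(X ≥ 6) with X binomial. The true change rate is not in the documents, so two values are shown.

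| True change rate in Group A | n=325 per arm | n=650 per arm |
|---|---|---|
| 1% | 11% | 63% |
| 2% | 63% | 99% |

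**4. Direction.** Suppose 25 Group A patients move from biopsy to no biopsy and 25 move the other way. The planned test sees 50/650 against 0/650, p ≈ 7×10⁻¹⁶. Final plans could still be identical in the two arms, for example 455/650 with a plan to biopsy in each (p=1.0).

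**5. What the alternatives deliver.**

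*Within Group A, human read.* Wilson 95% intervals at n=650 for assumed change rates: 10% (65/650), 7.9–12.5%; 20% (130/650), 17.1–23.2%; 30% (195/650), 26.6–33.6%. These are best cases, because a patient with no Lugol's-abnormal area and no visible lesion has no plan to change.

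*Within Group A, machine read.* G1 expects 400–500 subjects remaining at the revision. If they are split equally between arms (assumption), Group A has 200–250. At an assumed 20% rate the interval is 15.0–26.1% (40/200) or 15.5–25.4% (50/250).

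*Randomised comparison of final plans.* The largest 95% half-width for a difference is 1.96 × √(0.5/n): 5.4 points at n=650, 8.8 at n=250 and 9.8 at n=200.

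**The case against.** The strongest reply is that the endpoint is not broken. G2 already plans a 95% confidence interval for the proportion with a changed decision, and in Group A that interval answers the question in section D. This stands: the defect is confined to the added test sentence and to the interval not being tied to Group A. A reader might infer that the plan has no usable measure of clinical impact; the documents do not support that.

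Second, the wording of section D may mean comparing decisions between arms, in which case the chi-square test is sound and G2 is only loosely phrased. That may be the intent, but G2 specifies a change in the decision, and a comparison of final plans is a different quantity. If it is meant, it should be stated.

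Third, G2 refers to change resulting from Lugol's alone, so some Group B change may have been envisaged. A plan recorded under white light before Lugol's would supply one, but none is described, and it would measure Lugol's against white light rather than HRME. Figure 2 and the data collection form are not available, and either could show a further Group B decision point. A reader might infer that no second Group B plan exists; the documents support only that none is described.

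Fourth, plans are recorded per area while the endpoint is per patient, and G2 gives neither a rule for combining areas nor a denominator. That is missing detail in a short ethics-form section rather than an error. Likewise, ignoring direction is consistent with an objective that asks only whether decisions change. Tables by direction and histology would be useful additions, not corrections.

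**Conclusion.** The point holds for the between-arm test of change. On the text available, Group B's change rate is zero or undefined and the test reduces to asking whether Group A's rate exceeds zero. Six changed patients settle that question, and at 650 per arm a true rate of 2% would do so 99% of the time. The structural conclusion needs no assumed rate. The figures rest on about 650 per arm, two-sided 0.05 and Group B counted as zero.

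This is a secondary analysis with no stated decision rule. A reader might infer that it weakens the trial's main conclusions. It does not: the sensitivity and specificity tests in the surveillance group and the negative predictive value test in the screening group do not use these plans-changed data. The correction should be made, but it is one of wording and definition.

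**What to change.** In G2 (Clinical impact):

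- Delete the chi-square or Fisher comparison of change between arms.
- Keep the 95% confidence interval already planned, and define it as the proportion of Group A patients whose plan changed from the Lugol's plan. Report it separately for the human read and for the machine read, the latter in post-revision patients only.
- If a randomised comparison is wanted, compare recorded final plans by arm (HRME-informed plan in Group A, Lugol's plan in Group B), not biopsies taken, and label it as a different quantity from change in decision. For the machine read, use Group B patients randomised over the same period.
- If a second Group B plan is in fact collected, describe it in F2 and say what it is compared with.

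The cost is a few sentences; F2 already records the plans. The downsides are that the within-Group-A estimate is not a randomised contrast, and that its first plan is made knowing an HRME read will follow. The human-read sample also assumes that both plans were recorded before the revision; if they were not, it shrinks to post-revision patients.

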Endoscope Sterilization Procedures: The microendoscope is sterilized immediately after each procedure per standard endoscope accessory reprocessing guidelines. Any proflavine on the surface of the microendoscope is completely removed in the reprocessing procedure. This procedure has been approved by the FDA.

Patient Follow-Up for All Patients: All patients will recover from their procedures according to standard practice and be discharged home. To determine the safety of the HRME using topical proflavine, all pre, intra and immediate post-procedure adverse events will be recorded. Each patient will also receive a phone call from the research coordinator or co-investigator within 7 days from the study procedure to check for any post-procedure complications. In addition, prospective data will be collected on all patients at years 1,3,5 following index exam to determine whether they have progressed to a more advanced state of neoplasia.

Pathology Sample collection: Obtaining Tissue Samples from International Study Sites-Standard Operating Procedure

Biopsies from CICAMS and Jilin will be collected on H & E slides from clinical tissue blocks of all detected esophageal, high grade dysplasia and neoplasia.

The fixed biopsies will be oriented/embedded in paraffin and sectioned to facilitate comparison between histology and HRME images. Afterwards the serial sections will be routinely stained with hematoxylin and eosin for histopathologic examination.

The biopsies or resected specimens (from EMR) obtained from the examined areas will be routinely processed and interpreted by two expert GI pathologists ([name]) using standardized WHO classification criteria. Both pathologists will arrive at a consensus diagnosis which will be the official study read (gold standard).

The histopathologic diagnosis for each biopsy will be recorded on a standardized data collection form. The two central study pathologists will be reading ALL the specimens from China and the US and giving a consensus diagnosis. Image analysis will be performed comparing the actual histopathologic images to the "optical" images to develop image analysis algorithms and, potentially, image interpretations software. Rice University will be assisting in development of the image analysis algorithms for future software development.

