Sample Size Calculation (This has NOT changed from original IRB): The sample sizes are calculated separately for the two risk groups (650 in surveillance group and 650 in screening group). Among the surveillance group, we want to test non-inferiority in sensitivity and superiority in specificity of LCE+HRME vs. LCE alone. The standard endoscopic evaluation using LCE has high sensitivity of about 95% but with low specificity at about 65%. Based on the preliminary data, we hypothesize that LCE+HRME has the sensitivity of at least 90% level, which is similar to that of LCE, but LCE+HRME would improve the specificity to 85%. With significance level of 0.05 and 80% power, we need 223 neoplastic patients and 65 benign patients in each arm (LCE and LCE+HRME) to conclude that LCE+HRME has similar sensitivity as LCE alone and had higher specificity than LCE alone. Hence, we need 446 neoplastic patients and 130 benign patients. The sample size calculation is based on the formula in Pepe (Chapter 8, The statistical Evaluation of Medical Tests for Classification and Prediction, 2003).

According to the preliminary results, greater than 80% patients in the surveillance group would have neoplasia. We anticipate the enrollment of total 650 patients in the surveillance group to ensure the accrual of 446 neoplastic patients and 130 benign patients.

In screening group, we will study the accuracy of LCE+HRME for the diagnosis of neoplasia, and test whether the negative predictive value (NPV) of LCE+HRME is higher than LCE alone. The NPV for using LCE alone is about 95%. We hypothesize that the NPV for LCE+HRME should be at least 99% to be useful. A sample of 300 per arm would provide 82.1% power for this hypothesis with a 5% type-I error. Assuming an 8% loss to follow-up or incomplete data, we need to recruit 325 subjects per arm in the screening population.

Power Calculation (Augmented Reality HRME Revision): We anticipate having at least 400-500 subjects remaining by the time the Augmented Reality HRME revision IRB is approved and funding from the NCI obtained. With 400 patient Augmented Reality HRME data, assuming an accuracy of 83% AND 650 LC patient, assuming an accuracy of 57%, the study should have >93% power to detect a statistically significant difference with an alpha error rate of 0.05.

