For the HRME image interpretation study, the sample size of 10 endoscopists was selected based on a prior power analysis based on non-inferiority. The 10 endoscopists will review about 140 HRME images. It is hypothesized that software interpretation of the HRME images will be non-inferior to the endoscopist interpretation. Non-inferiority is defined as a 10% difference in specificity between the two groups with 90% power and alpha of 0.05.

G2. Data Analysis

Provide a description of your plan for data analysis. State the types of comparisons you plan (e.g. comparison of means, comparison of proportions, regressions, analysis of variance). Which is the PRIMARY comparison/analysis? How will the analyses proposed relate to the primary purposes of your study?

Among the surveillance group, three analyses in testing the null hypotheses will be performed, including two interim analyses and one final analysis. The analysis will be performed when 220, 440 and 650 study subjects have been accrued, respectively.

The interim analysis will use a symmetric two sided group sequential design using a Hwang-Shih-DeCani spending function with beta spending of .4, which provides an O'Brien-Fleming-like conservative upper bound. This approach requires a two sided significance level of 0.0026 and 0.0114 for the interim analysis and 0.0464 for the final analysis of overall survival.

There will be no interim analysis for the screening population.

The primary analysis for the surveillance group is to test non-inferiority in sensitivity and superiority in specificity of LCE+HRME vs. LCE alone. The test statistic is based on the formula in Pepe (Chapter 8, The statistical Evaluation of Medical Tests for Classification and Prediction, 2003). Additionally, sensitivity and specificity of LCE+HRME vs. LCE alone will be estimated on a per patient basis with 95% confidence intervals. The primary goal for the screening group is to test whether the negative predictive value (NPV) of LCE+HRME is higher than LCE alone. This is done using Fisher's exact test. Additionally, the negative predictive value will be summarized with 95% confidence intervals.

The secondary analysis includes diagnostic yield, clinical efficiency, clinical impact, progression rate, and the rate of adverse events.

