Subjects will be consented on the day of their procedure. Subjects will be taken to a private area where the study information will be discussed. No additional sensitive information will be requested from the subjects beyond what is required to perform a standard surveillance endoscopy. Subjects will be given an ID number for all forms, images, and communications. All data will be coded. Source documents will be redacted of all PHI before being sent from outside sites for data monitoring/data entry in the database. All PHI collected on BCM subjects will be stored in locked cabinets or password-protected files/computers where only the PI and study coordinator can see the names. All case report forms will use the assigned subject ID. Since the subject participation is only for one visit, there will be limited opportunity for privacy interests to arise between study recruitment and end of the study. The only extra intrusion of privacy will be an additional phone call within 7 days of the procedure to ensure that the subject has not suffered any adverse events. During the follow-up, only the study coordinator and/or the PI will have contact with the subject. Information pertaining to the study will only be discussed with the subject and messages containing identifiers of the subject's participation will not be left on voice-mail messages.

For the post hoc image analysis project, the risk to the research subjects are minimal. Loss of privacy is an inherent risk, but to mitigate this, each subject will be assigned an unique, random ID and any identifying information will not be stored.

H2. Data and safety monitoring plan

Do the study activities impart greater than minimal risk to subjects?

Yes

NOTE: The answer to the questions in H2 requires the completion of the form: 'Section H – Data and Safety Monitoring Plan' as an attachment in Section S.

H3. Coordination of information among sites for multi-site research

Is the BCM Principal Investigator acting as the SPONSOR-INVESTIGATOR for this multi-site research?

Yes

Is BCM the COORDINATING CENTER for this multi-site research?

Yes

If the answer to EITHER of the questions above is "Yes", please complete the following questions:

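### Five-year progression is compared by chi-square or Fisher's exact test, but the plan does not say how patients without a year-5 status are counted

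*Combined protocol and SAP*

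**What the plan says.** Section G2 (Data Analysis) ranks progression among the secondary analyses: "The secondary analysis includes diagnostic yield, clinical efficiency, clinical impact, progression rate, and the rate of adverse events". Its paragraph on progression rates sets the horizon, "Five year follow-up of progression rates to more advanced pathology or esophageal cancer (EC) in the 2 arms will be conducted", and then the method, "Progression rates and their 95% confidence interval will be summarized and compared between LCE+HRME and LCE alone by the chi-square test". The alternative named there is Fisher's exact test.

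The observation times are in section F2 (Procedure), under patient follow-up: "prospective data will be collected on all patients at years 1,3,5 following index exam to determine whether they have progressed". Progression in that sentence means worsening neoplasia.

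The plan does not say:
- whether the rate is a five-year proportion, or what its denominator is;
- how patients who are lost, who die, or who have not reached year 5 at analysis are counted;
- any censoring, missing-data or sensitivity method for this endpoint;
- that the comparison is stratified by risk group, although G2 does stratify diagnostic yield and procedure time.

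The only loss allowance is in section G1, for the screening group's negative predictive value: "Assuming an 8% loss to follow-up or incomplete data, we need to recruit 325 subjects per arm in the screening population". The privacy text in section H1 gives a different picture of the length of participation: "Since the subject participation is only for one visit", with one telephone call within 7 days as the only extra contact.

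**The concern.** A two-by-two test needs one settled status per patient. A patient last seen free of progression at year 1 or year 3 has no settled five-year status. The plan gives no rule, so the analyst must choose one, possibly after seeing the data. Three simple rules are available:

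1. Count lost patients as progression-free. Progression that happens after loss is missed, so the rate is too low.
2. Use every patient with known status, meaning those seen to progress at any visit plus those seen free at year 5. Early events stay in while early losses without an event drop out, so the rate is too high.
3. Use year-5 attenders only. This is unbiased if loss is unrelated to progression, but it discards progression already recorded in patients who were lost later.

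At stake are the reported five-year rates and, if loss differs by arm in amount or in its relation to progression, the arm comparison itself. The primary tests of sensitivity, specificity and negative predictive value are not touched.

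**Working it through.** **The plan's own figure.** There is none for progression: no rate, loss, power or sample size. The 8% in G1 belongs to the screening group's negative predictive value (325 × 0.92 = 299, against the 300 per arm required there).

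**Inputs from the documents.** Visits at years 1, 3 and 5 (F2). 1,300 patients, 650 in each risk group, with 325 per arm stated for screening (G1). That makes 650 per arm over both risk groups if allocation is 1:1 throughout.

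**Assumptions.** True five-year progression p, the same in both arms: 20%, varied from 5% to 30%. Five-year loss L: 0% to 40%. Constant progression and loss hazards, with loss independent of progression.

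**Formulas.** S(t) = (1−p)^(t/5) is the probability of being progression-free at t. G(t) = (1−L)^(t/5) is the probability of still being followed at t.
- Seen to progress: D = [1−S(1)]G(1) + [S(1)−S(3)]G(3) + [S(3)−S(5)]G(5). This is the rate under rule 1.
- Known status: K = D + S(5)G(5). The rate under rule 2 is D/K.
- Year-5 attenders only: [1−S(5)]G(5)/G(5) = p.

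**Worked case, p = 20%, L = 30%.** S = 0.9564, 0.8747, 0.8000 and G = 0.9311, 0.8073, 0.7000 at years 1, 3 and 5.
- D = 0.0406 + 0.0659 + 0.0523 = 0.1589, so rule 1 gives 15.9%.
- K = 0.1589 + 0.8 × 0.7 = 0.7189, so rule 2 gives 0.1589/0.7189 = 22.1%.
- Rule 3 gives 20.0%, but uses only 0.2 × 0.7 = 0.1400 of the 0.1589 observed progressions. It discards 0.0189/0.1589 = 12% of them.
- With L = 0 all three rules give 20.0%, so the visit schedule alone causes no bias.

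**False-positive rate** of the two-sided 5% chi-square test when the arms truly do not differ: Φ[(d − 1.96·se₀)/se₁] + Φ[(−d − 1.96·se₀)/se₁]. Here d is the absolute difference in expected rates, and se₀ and se₁ are the pooled and unpooled standard errors. For 20% v 40% loss under rule 1 with 650 per arm: d = 0.1729 − 0.1443 = 0.0286, se₀ = 0.0203, se₁ = 0.0202. The first term is Φ(−0.55) = 0.29 and the second is negligible.

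Results for p = 20%:

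| Loss, arm v arm | Rule 1 rates | False positives, 650 / 325 per arm | Rule 2 rates | False positives, 650 / 325 per arm |
|---|---|---|---|---|
| 8% v 8% | 18.9% both | 5.0% / 5.0% | 20.5% both | 5.0% / 5.0% |
| 30% v 30% | 15.9% both | 5.0% / 5.0% | 22.1% both | 5.0% / 5.0% |
| 8% v 20% | 18.9% v 17.3% | 12.0% / 8.4% | 20.5% v 21.3% | 6.3% / 5.7% |
| 10% v 30% | 18.7% v 15.9% | 26.3% / 15.5% | 20.6% v 22.1% | 9.3% / 7.1% |
| 20% v 40% | 17.3% v 14.4% | 29.2% / 16.9% | 21.3% v 23.1% | 10.4% / 7.7% |

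Rule 3 stays at 20.0% in both arms throughout. For 20% v 40% loss and 650 per arm, other true rates give, under rule 1 or rule 2: 10.3% or 6.6% (p = 5%), 16.2% or 8.0% (p = 10%), 43.2% or 12.5% (p = 30%).

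**With a life-table estimate.** Each interval uses only patients free at the previous visit and seen at the next, so G cancels. For year 3, [S(1)−S(3)]G(3) / [S(1)G(3)] = 1 − 0.8747/0.9564 = 0.0854. The interval risks are 0.0436, 0.0854 and 0.0854, and 1 − 0.9564 × 0.9146 × 0.9146 = 20.0% in each arm, whatever the loss. Events found at years 1 and 3 are all used.

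**The case against.** The case for leaving the plan alone has weight. Nothing in the documents shows that five-year loss will be large or will differ by arm. Follow-up applies to all patients, and F2 has every Lugol's-abnormal area biopsied in both arms. At 8% equal loss the rate moves only to 18.9% or 20.5% and the test is exact in level. Analysing year-5 attenders alone would be unbiased under the model used here. Progression is secondary, with no hypothesis or power attached. All of this stands, and it limits the point to an unstated rule and a better method.

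A reader might infer more, and the documents do not support it:
- **That observing status only at years 1, 3 and 5 biases the rate.** It does not. With complete follow-up, the year-5 visit gives the five-year proportion.
- **That lost patients must be handled in a biased way.** Rule 3 is a counterexample when loss is unrelated to progression. Its cost is lost information.
- **That H1 shows loss is likely.** It is application text on privacy risk, not shown to be given to subjects, and it goes on to mention contact during follow-up. It conflicts with F2 and needs reconciling, but it is not evidence of attrition.
- **That the test will be wrong about 29% of the time.** That figure needs 20% v 40% loss, the denominator most sensitive to it, 20% progression and pooled arms of 650. It falls to 10.4% under rule 2 and to 16.9% at 325 per arm.
- **That a censored-data method cures the problem.** It does so only if loss is unrelated to progression.

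**Conclusion.** The point holds as a gap in the analysis of a secondary endpoint that is worth closing. The named tests assume a complete five-year status, and the plan has no rule for patients without one.

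Under the assumed 20% progression and non-informative loss, equal loss of 8% to 30% shifts the reported rate down to between 18.9% and 15.9%, or up to between 20.5% and 22.1%, depending only on the denominator. The test's level is unaffected. A false arm difference needs loss that differs by arm, in amount or in its relation to progression. For 8% v 20% up to 20% v 40%, with 650 per arm, the false-positive rate is 12% to 29% if lost patients count as progression-free and 6% to 10% with known status.

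The progression and loss rates and the constant hazards are assumptions, and 650 per arm presumes 1:1 allocation. What rests on the documents alone is that the status rule is missing, the test presupposes it, and the follow-up already planned supports a method that does not.

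**What to change.** In the progression paragraph of G2:

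- Estimate cumulative five-year progression by arm with a discrete-time (life-table) or interval-censored method using the year 1, 3 and 5 visits, with 95% confidence intervals.
- Compare the arms with the matching test, stratified by risk group (screening, surveillance).
- State how deaths and patients not yet at year 5 are counted.
- Report completeness of follow-up at each visit by arm.
- Add a sensitivity analysis for loss related to progression.

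Separately, reconcile the one-visit statement in H1 with the follow-up in F2.

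The cost is a few sentences in the plan and somewhat more analysis work, with no new visits, patients or data items. The main analysis would then rely on non-informative loss, which the sensitivity analysis is there to examine.
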